## 4.6 Study Periods

### Screening period

The Screening period will be defined as the period from informed consent signature date to the first IMP intake date.

### Dose finding period

The dose finding period will be defined as the period from the date of the first IMP intake to the day before visit D3 or the day before IMP down-titration.

The dose finding period will be split into **dose toleration periods** for each dose prescribed for that period. The period will start from the date of the IMP taken at the site at visit A1/A3/B3/C3 to the day before visit A3/B3/C3/D3 or the day before IMP down-titration.

### Maintenance period

The maintenance period will be defined as the period between visit D3 or the date of IMP down-titration and the date of the last IMP intake until MPV3 (including the first day of visit). For patients participating in the extension study, the end of the maintenance period will be the end date of visit MPV3.

### Down-titration period

The down-titration period is only applicable to patients not participating in the extension study and with an IMP dispensation at visit MPV3/EDV.

The down-titration period will be defined as the period starting on the second day of MPV3 or one day after visit EDV until the date of the follow-up visit for down titration (FUV1).

### Follow-up period

The follow-up period is only applicable to patients not participating in the extension study.

The follow-up period will be defined as the period between the day after the last IMP intake until the date of study termination.

### Early discontinuation

For patients who discontinue the study early, the EDV date will be the end date of any ongoing study period.

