9.4.2 Withdrawals

Patients who have been enrolled and, for whatever reason, discontinue the study after first IMP intake at visit A1 are classified as withdrawals. Patients may withdraw from the study at any time, either on their own request or at the discretion of the investigator.

Reasons for withdrawal must be documented carefully in the patient's medical records and in the eCRF. Investigators must attempt to contact patients who fail to attend scheduled visits by telephone, letter, visit, etc., to exclude the possibility of an AE being the cause. Should this be the case, the AE must be documented, reported and followed up as described in Section 12. Attempts to contact the patient must be documented in the patient's medical records. The project leader and the medical monitor of the study at Bial will be informed of each withdrawal and the reason for it. To minimize the loss to follow-up, the specified patient's family member/friend (if available) will be contacted. An early discontinuation visit (EDV) (see Section 11.6.7) should be performed within 10 days, if possible, on each withdrawal. However, in case of early discontinuation due to withdrawal of consent, the patient will have the right to refuse this additional visit and phone calls and no further data will be collected for this patient apart from the reason for discontinuation. The investigator should attempt to retrieve all IMPs from all patients.

Patients may withdraw or may be withdrawn from the study for the following reasons:

- At their own request (withdrawal of consent)
- If in the investigator's opinion, for reasons of safety or ethics, continuation in the study would be detrimental to the patient's well-being
- Pregnancy
- Ineligibility/development of an exclusion criterion
- In case of an intolerable adverse event(s)
- At the specific request of the sponsor
- Lost to follow up
- Other reasons

Patients who are withdrawn are not to be replaced.

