Urinalysis	●			●	●		●		●
Physical examination	●			●	●	●	●		
12-lead electrocardiogram	●	● 		●	●	●	● 		●
Number of digital scars 	●			●	●	●	●		
Modified Rodnan Skin Score 	●						●		
Blood pregnancy test 	●								
Urine pregnancy test 		●		●	●	●	●		●
Arterial blood gas analysis 		●					● 		
Efficacy									
SF-36v2	●						● 		
6-min walk test/Borg dyspnoea score	● 						● 		
Echocardiography	●						● 		
Right heart catheterisation 		●					● 		
Blood withdrawal biomarker	●						● 		

1. EDV = early discontinuation visit. An EDV has to be performed within 10 days of early discontinuation. Additionally, patients who will not participate in the extension study will be contacted by phone at the time of last patient's last visit (LPLV) to document their vital status.

2. Patients will be hospitalised for 24 hours.

3. The dose will be increased if the previous dose was considered safe by the investigator according to safety criteria (at A3, B3 and C3).
4. Blood samples for PK and PD to be taken prior to IMP intake as well as 1, 2, 4, 8, 16 and 24 hours after IMP intake (but still prior to next IMP intake).
5. The patient has to be advised not to take the IMP at home on the day of A3, B3, C3, D3, MPV1, MPV2 and MPV3.
6. Only in women of childbearing potential.
7. Only applicable in patients taking 150 mg or 200 mg zamicastat and who will not participate in the extension study. In case a patient will discontinue the study early due to the occurrence of an AE, down-titration is not mandatory, but at the investigator's discretion.
8. Not applicable at EDV.
9. Visits during the Dose-finding period:
  - Dose A (50 mg zamicastat):** visits A1, A2 and A3
  - Dose B (100 mg zamicastat):** visits B2 and B3. These visits will only be performed if the patient was up-titrated to 100 mg zamicastat at A3.
  - Dose C (150 mg zamicastat):** C2 and C3. These visits will only be performed if the patient was up-titrated to 150 mg zamicastat at B3.
  - Dose D (200 mg zamicastat):** D2 and D3. These visits will only be performed if the patient was up-titrated to 200 mg zamicastat at C3.If the patient's next dose will not be tolerated, the patient will be asked to come to an unscheduled visit (UV) and he/she will be down-titrated to his/her previous dose.

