## 5.4 Exposure to IMP and Compliance

### 5.4.1 Exposure to IMP

Exposure data from the eCRF include:

- First IMP intake
- Last IMP intake before the visit (except unscheduled visits)
- IMP intake at the site (except unscheduled visits)
- Last IMP intake (for withdrawals and patients that do not participate in the extension study)
- Date of IMP down-titration

The overall treatment duration in days will be calculated as follows:

$$\text{Overall treatment duration (days)} = \text{last IMP intake date} - \text{first IMP intake date} + 1$$

The following definitions will be used to calculate the overall treatment duration:

- **The date of the first IMP intake** is the date of the IMP intake as recorded at visit A1.
- **The date of the last IMP intake** depends on the patient's decision to participate in the extension study. If the patient is not participating in the extension study, then the last IMP intake is the date of the last intake recorded at the study termination page. If the patient is participating in the extension study, then the on-site IMP intake at MPV3 will be the date of the last IMP intake.

The duration of the study periods in days will be calculated as follows:

$$\begin{aligned} \text{Treatment period duration (days)} \\ = \text{treatment period end date} - \text{treatment period start date} + 1 \end{aligned}$$

See Section 4.6 for definitions of study periods.

Overall and by-period treatment duration will be adjusted in the case of occurrence of adverse events with associated IMP interruption periods. The calendar days between and including start and stop dates of IMP interruptions will not count towards treatment duration.

The following statistical output will be provided:

Table 15.1.9.1.1 Treatment Duration (days) – Safety Set

Table 15.1.9.1.2 Treatment Duration (days) – Full Analysis Set

Table 15.1.9.1.3 Treatment Duration (days) – Pharmacokinetic Analysis Set

The default summary statistics of treatment duration will be presented by HTD and overall.

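### For patients who stop drug during dose finding, by-period treatment duration runs to the early discontinuation visit and can count days after the last tablet

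*SAP*

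**What the plan says.** SAP 4.6 defines the study periods.

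- **Dose finding** runs "from the date of the first IMP intake to the day before visit D3 or the day before IMP down-titration". It is split into dose toleration periods, each of which ends the day before the next dose-step visit or the day before down-titration.
- **Maintenance** ends at "the date of the last IMP intake until MPV3".
- **Follow-up**, for patients not entering the extension: "The follow-up period will be defined as the period between the day after the last IMP intake until the date of study termination".
- **Down-titration** applies only when IMP is dispensed at MPV3 or the EDV. After an EDV it starts one day later.
- **Early discontinuation**: "the EDV date will be the end date of any ongoing study period".

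On the timing of the visit, footnote 1 of the SAP schedule says "An EDV has to be performed within 10 days of early discontinuation". Protocol 9.4.2 is softer: the visit "should be performed within 10 days, if possible, on each withdrawal". It also lets a patient who withdraws consent refuse the visit.

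SAP 5.4.1 gives two durations. Overall treatment duration is last intake minus first intake plus 1. By-period duration is period end minus period start plus 1, with the dates taken from Section 4.6. One correction is made to both: "Overall and by-period treatment duration will be adjusted in the case of occurrence of adverse events with associated IMP interruption periods". It removes the days between the recorded start and stop of an interruption.

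**The concern.** A period duration labelled as treatment should not contain days on which the patient had already stopped treatment for good. The interruption correction does not remove those days, because it deals with interruptions that have a start and a stop linked to an adverse event.

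Three things are at stake. One period can come out longer than the patient's whole treatment, so the two durations defined in SAP 5.4.1 contradict each other. The same calendar days belong to two periods. And SAP 5.6.1 shows treatment-emergent events by dose finding, maintenance and down-titration period, so the end date also decides where an event that starts after the last tablet is displayed.

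Patients who do not tolerate 50 mg must be withdrawn and are shown in a separate No HTD group (SAP 2.5 and 4.3). In a small group of that kind, a by-period mean would have few unaffected patients to dilute the excess.

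**Working it through.** The plan gives no figure to reproduce, so this is date arithmetic with the SAP's own formulas.

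**Inputs**

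- Period and overall duration formulas: SAP 5.4.1.
- Period end for an early discontinuer in dose finding: the EDV date (SAP 4.6), because neither D3 nor a down-titration takes place.
- Follow-up start: the day after last intake (SAP 4.6).
- Gap *g* from last intake to EDV: assumed to be 0, 1, 5 or 10 days. The 10-day window runs from discontinuation, not from the last tablet, and is a target in the protocol, so 10 is illustrative and not a strict maximum.
- No IMP is dispensed at the EDV, and the patient is still in the study at the EDV.

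**Formulas**

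- Excess = (EDV − start + 1) − (last intake − start + 1) = EDV − last intake = *g*.
- Overlap with follow-up = EDV − (last intake + 1) + 1 = *g*.

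**Results: dose-period duration in days, by gap**

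| Patient | Overall duration | *g* = 0 | *g* = 1 | *g* = 5 | *g* = 10 |
|---|---|---|---|---|---|
| Dose A, last intake Day 5 | 5 | 5 | 6 | 10 | 15 |
| Dose A, last intake Day 10 | 10 | 10 | 11 | 15 | 20 |
| Dose C from Day 29, last intake Day 35 | 35 | 7 | 8 | 12 | 17 |

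In the first row with *g* = 10, the Dose A period is 15 − 1 + 1 = 15 days and overall duration is 5 − 1 + 1 = 5 days. Days 6 to 15 lie in both dose finding and follow-up. In the third row with *g* = 10, the periods sum to 28 + 17 = 45 days against an overall duration of 35. Ten days is 10/14 = 71% of a nominal dose period.

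**Effect on a mean.** If *k* of the 32 planned patients stopped in Dose A with a 10-day gap, the mean Dose A duration would rise by 10*k*/32 days: 0.3 for *k* = 1, 0.9 for *k* = 3, 1.9 for *k* = 6. These values of *k* are assumptions.

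**Maintenance.** Suppose a patient starts maintenance on Day 57 and takes the last tablet on Day 76. The period's own definition gives 76 − 57 + 1 = 20 days. Only if the EDV rule overrode that definition would a 10-day gap give 30. The SAP does not say which governs, but a period that has already closed is not naturally read as ongoing.

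**Follow-up.** Read literally, the EDV rule also closes follow-up, which is the ongoing period once dosing has stopped. In the first example that would be Day 15, yet Protocol 11.6.9 plans a follow-up visit for early discontinuers 14 days after last intake, nominally Day 5 + 14 = Day 19.

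**The case against.** The strongest reply is that the effect is narrow, and much of that reply stands.

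- A reader might infer that total exposure is overstated. It is not: overall duration stops at last intake, and its excess is 0 days in every case above.
- A reader might infer that maintenance durations are inflated too. The maintenance definition already ends at last intake, and the EDV rule can be read as a fallback for periods that would otherwise have no end.
- A reader might infer that the distortion sits where higher doses are not tolerated. Patients not tolerating 100, 150 or 200 mg are normally down-titrated and enter maintenance, and their dose period closes the day before. Withdrawal for intolerance is prescribed at 50 mg or during maintenance. The Dose C row above is possible, since patients may leave for other reasons, but it is not the planned route.
- A reader might infer that adverse event rates are distorted. Dose attribution uses the prescribed dose at onset, percentages use the safety set, and onsets up to 14 days after last intake are included on purpose. Only the period under which an event is shown can change.
- Drug-free days are conditional. A patient who takes tablets up to the EDV has none. If down-titration IMP is dispensed at the EDV, last intake comes later and the overlap with follow-up does not arise.
- SAP 5.4.1 defines by-period duration, but its table text promises treatment duration only by HTD and overall. The table shells are not available, so where the by-period figures will appear cannot be confirmed.

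None of this removes the dose-finding case. There the definitions overlap as written, and no stated adjustment takes the days out.

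**Conclusion.** The point holds for patients who stop IMP during dose finding and attend a later EDV. Their by-period treatment duration exceeds time on drug by the gap between last tablet and EDV, which is 0 to 10 days under the assumed range, and the same days also count as follow-up. The 10-day case rests on an assumed gap, and the documents do not say how many patients would be affected.

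For maintenance the finding is only that precedence is unstated. Overall duration is unaffected, as are the efficacy summaries.

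A reader might also infer that by-period compliance in SAP 5.4.2 is wrong for these patients. That would follow only if the length of the dose prescription were programmed to run to the period end, which the SAP does not say.

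This is an inconsistency that should be corrected. It does not threaten the study's conclusions.

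**What to change.** Add to SAP 4.6, with a cross-reference in 5.4.1:

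*For treatment-duration derivations, the ongoing dose toleration, dose finding or maintenance period of an early discontinuer ends on the date of the last IMP intake in that period, whether or not an EDV takes place. This takes precedence over the EDV rule. The EDV rule does not end the follow-up period.*

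Leave the start of the down-titration period as it is, one day after an EDV at which IMP is dispensed. Keep EDV assessments under the EDV visit label.

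Do not simply move post-stop events to follow-up in Tables 15.3.1.1 to 15.3.1.9. Those displays list dose finding, maintenance, down-titration and the whole trial, so the events would vanish from every listed period. Either keep treatment-emergent events that start after last intake under the last treatment period with a footnote, or add a post-treatment column.

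The cost is a few sentences, one derivation change and a footnote or column in the event tables. No new data are needed: SAP 5.4.1 already lists the final intake for withdrawals and the last intake before each scheduled visit. If outputs have already been produced, the change can be described and justified in the final report, as Protocol 13.5 provides.

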## 4.7 Baseline Value

### Baseline value

The baseline value for a variable is defined as the last non-missing value collected before the first IMP intake, unless otherwise specified.

See section 5.4.1 Exposure to IMP for definition of first IMP intake.

**Absolute change from baseline** will be calculated as

$$\text{Absolute Change from Baseline at Visit } X = \text{Value at Visit } X - \text{Baseline Value}$$

## 4.8 Visit Windows

Data will be analysed with the nominal visit number.

## 4.9 Coding Systems and Conventions

### 4.9.1 Coding of adverse events and medical history

Adverse event and medical history investigator terms are assigned to a lowest level term (LLT) and a preferred term (PT) and will be classified by high level term (HLT), high level group term (HLGT) and system organ class (SOC) according to the Medical Dictionary for Regulatory Activities (MedDRA), Version 22.0 or higher.

### 4.9.2 Coding of medications

Medications are classified according to active drug substance using the WHO Drug Global dictionary, version 2019, March, or higher. The WHO drug code has 11 digits. The generic name is defined by the first 6 of the 11 digits. In addition, the Anatomical Therapeutic Chemical (ATC) classes are assigned to the drug code. In this study, ATC codes are defined to the 4th level.

## 4.10 Handling of Missing Data

No imputations of missing data are planned for this study.

## 5 STATISTICAL ANALYSIS: DEFINITIONS, DERIVATIONS, CALCULATIONS AND METHODOLOGY

### 5.1 Patient Disposition

#### 5.1.1 Disposition and Withdrawals

The following disposition data will be collected in the electronic case report form (eCRF):

- date of informed consent
- date of study termination
- did the patient complete the study as scheduled (yes, no)
- will the patient participate in the extension study (yes, no)
- reason for premature study termination

**Screening failures** will be all patients who have been enrolled in the study (i.e. ICF signed) but discontinued the study before the first IMP intake at visit A1 due to whatever reason (withdrew consent, did not fulfil eligibility criteria, decision of investigator, etc.).

**Withdrawals** will be all patients who have been enrolled and, for whatever reason, discontinued the study after the first IMP intake at visit A1. Patients may withdraw or may be withdrawn from the study for the following reasons:

- At their own request (withdrawal of consent)
- In the investigator's opinion, for reasons of safety or ethics, continuation in the study would be detrimental to the patient's well-being
- Pregnancy
- Ineligibility/development of an exclusion criterion or inclusion criterion no longer fulfilled
- Intolerable adverse event(s)
- At the specific request of the sponsor
- Major protocol deviations
- Patient non-compliance
- Lost to follow up
- Other reasons

Study completion status will be determined by patient's decision to participate in the extension study. If the question "Will the patient participate in the extension study?" in the eCRF is answered as "Yes", the patient will be considered as a completer. If the patient does not participate in the extension study, then the completion status will be based on the Study Termination page in the eCRF.

The following statistical output will be provided:

#### Table 15.1.1.1 Analysis Sets – Enrolled Set

Number and percentage of patients included into the enrolled, safety, full analysis, modified full analysis, pharmacokinetic, and pharmacodynamic analysis sets will be provided.

#### Table 15.1.1.2 Reasons for Exclusions from Analysis Sets – Safety Set

Number and percentage of patients excluded from the full analysis, modified full analysis, pharmacokinetic, and pharmacodynamic analysis sets will be provided. Percentages will be based on the number of patients in the safety set. The reasons of exclusion from the analysis sets will be incorporated into the table.

#### Table 15.1.2 Screening Failures – Enrolled Set

Counts and percentages of patients who discontinued the study during the screening phase prior to enrolment to the treatment period will be summarised by reasons associated with the discontinuation. Percentage will be based on the number of patients in the enrolled set.

#### Table 15.1.4 Patient Disposition – Safety Set

Counts and percentages of patients who completed the treatment period as scheduled, withdrawals during the treatment period will be summarised by HTD and overall. Reasons associated with the termination will be included. Percentage will be based on the number of patients in the safety set.

Table 15.1.5.1.1 Number of Patients by Country and Site – Enrolled Set

Table 15.1.5.1.2 Number of Patients by Country and Site – Safety Set

Counts and percentages of patients will be presented by country and by site. Percentage will be based on the number of patients in the specified set.

Table 15.1.5.2 Number of Patients by Visit – Safety Set

Counts and percentages of patients who continue the study will be presented by visit. Percentage will be based on the number of patients in the safety set.

Listing 16.2.1.1.1 Patient Disposition – Safety Set

Patients who enter the treatment period and complete the study as scheduled or as withdrawals will be listed. Reasons for premature study termination will be displayed for withdrawals.

Listing 16.2.1.1.2 Screening Failures – Enrolled Set

Patients who discontinued the study during the screening phase prior to enrolment to the treatment period will be listed. Reasons associated with the discontinuation will be displayed.

Listing 16.2.1.2 Patient Visits – Enrolled Set

All visit dates will be listed by patient.

Listing 16.2.1.4 Exclusions from Analysis Sets – Enrolled Set

Patients excluded from any analysis set and corresponding reasons for exclusion will be listed.

Figure 15.1.1 Flow Chart of Patient Disposition – Enrolled Set

Number of patients will be displayed in flow chart by their disposition.

Figure 15.1.2 Flow Chart of Analysis Sets – Enrolled Set

Number of patients will be displayed in flow chart by analysis sets.

## 5.1.2 Protocol Deviations

Protocol deviations are deviations from the procedures outlined in the clinical study protocol or from subsequent protocol-related instructions like missed evaluations, incorrect timing of evaluations, non-compliance with IMP and intake of prohibited medications or any non-adherence to the clinical study protocol that impacts patient's rights, safety or welfare. Protocol deviations that may affect the pharmacokinetic and pharmacodynamic outcomes will be discussed during the Data Review Meeting (DRM).

In addition, the study disruption due to the COVID-19 pandemic will be assessed in terms protocol deviations and discussed during the DRM. A separate listing for patients affected by the COVID-19 related study disruption will be provided.

Details regarding the DRM will be provided in Section 6.

The following statistical output will be provided:

Table 15.1.3 Major Protocol Deviations – Safety Set

Number and percentage of patients with major protocol deviations will be summarised by HTD and overall. Protocol deviations will be summarised during the dose finding and maintenance periods and overall. Percentage will be based on the number of patients in the safety set.

Listing 16.2.1.3.1 Major Protocol Deviations – Safety Set

Patients with major protocol deviations will be listed.

Listing 16.2.1.3.2 Patients Affected by the COVID-19 Pandemic – Safety Set

Patients that were affected by the COVID-19 pandemic as well as the details of the deviation will be listed.

